## **Specific Aims**

This randomized controlled pilot study will characterize effects of SwallowSTRONG® Device-Facilitated Isometric Progressive Resistance Oropharyngeal (DF I-PRO) therapy in a dose response framework on swallowing-related outcomes in a group of unilateral ischemic stroke patients. These results will be used to determine adequate sample size in order to support a larger clinical trial focused on the efficacy of this therapy approach for improving swallowing safety. This randomized study will expand upon previous work examining effects of this therapy approach on swallowing and health-related outcomes now limited to a heterogenous cohort of Veterans with dysphagia from a variety of etiologies. It will focus specifically on patients post-stroke who have been shown to experience improvements in swallow function following DF I-PRO therapy.

**Specific Aim 1:** To determine differences in swallowing physiology and bolus flow measures a) between a group of unilateral ischemic stroke subjects undergoing SwallowSTRONG® DF I-PRO therapy and controls and b) between 8 and 12 weeks of treatment.

**Hypothesis 1a:** Subjects treated with DF I-PRO therapy at both treatment duration points will demonstrate greater improvements in swallow physiology (isometric and swallowing pressures) as well as bolus flow measures (levels of airway invasion, post-swallow residue/stasis, oral transit times, and stage transition duration times) as compared to the control group.

**Hypothesis 1b:** Subjects treated with DF I-PRO therapy will experience improvements in swallow physiology and bolus flow measures at the 12 week duration compared to 8 weeks.

**Specific Aim 2:** To examine changes in level of oral intake and swallowing quality of life in post-stroke patients undergoing DF I-PRO therapy as compared to a control group and as they relate to treatment duration response at 8 weeks and 12 weeks

**Hypothesis 2a:** Patients undergoing DF I-PRO therapy will require less restrictive diets and will report improved swallowing-related quality of life compared to those in the control group at both treatment duration points.

**Hypothesis 2b:** Twelve weeks of DF I-PRO therapy will result in greater improvements (least restrictive diets and improved quality of life) compared to the 8 week duration.

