## **Intervention**

Participants who meet criteria for dysphagia on the videofluoroscopic swallowing examination will be randomly assigned into one of two groups: 1) a control group that will be receiving compensatory treatments only or 2) 12-week DF I-PRO therapy *plus* compensatory treatments, such as thickened liquids and/or postural strategies during natural swallowing activities for 12 weeks. Patients will be enrolled and trained in DF I-PRO therapy by [name] who regularly uses the SwallowSTRONG®-facilitated I-PRO therapy in clinical practice or a UW Voice and Swallowing clinician involved in this study who has been adequately trained in DF I-PRO therapy. Regardless of the treatment group to which a subject is randomized, they will be evaluated in the hospital at baseline and 8-week time points. If a patient in either group no longer meets criteria for dysphagia (Penetration-Aspiration Scale score of 3 or higher OR a rating of 2 on the Residue scale in any location) on the 8-week videofluoroscopic swallowing examination, s/he will no longer continue participation in the study. If a patient in either group remains dysphagic at the 8-week visit, s/he will continue participation in the study through the 12-week assessment point. [name] or a UW Voice and Swallowing clinician will conduct the 8 and 12 week assessments.

**Group 1: Compensatory treatments only:** This group will receive standard swallowing intervention, which is identified by the SLP as appropriate to treat the patient's dysphagia and is common clinical practice. This group is not receiving experimental therapy. Their therapy may include: 1) modifying the foods the subject eats or the fluids s/he drinks; 2) changing his/her posture when eating or drinking (for example, by a simple chin tuck) or using a swallowing maneuver while eating or drinking; 3) having him/her eat more slowly or in a quiet environment to make swallowing easier and safer; or 4) performing range of motion or vocal exercises for

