**Group 2: SwallowSTRONG® device-facilitated I-PRO therapy plus compensatory treatments:**

[figure not shown]
Isometric tongue strengthening will be completed using the SwallowSTRONG® device (see Figure 1).

This device hand-held instrument provides numeric readout of pressure (hPa) and digital feedback of performance. It consists of a short cord (approx. 10 inches), which is attached to a small digital touch screen display. The 4-sensor array is custom-molded to the hard palate to ensure consistent placement.

Tongue press exercises consist of pressing the tongue against the sensors. Isometric exercises will focus on the anterior and posterior sensor. Subjects will be given a target pressure value for both the anterior and posterior sensor locations for which to aim during strengthening. Visual feedback on the display will signal the subject that they have attained their target pressure goal.

Prior to initiation of the strengthening regimen, baseline one repetition maximum (1RM) lingual pressures will be obtained at the anterior and posterior sensors independently by gathering 3 tongue press trials at each site that differ by less than 5% to adjust for variability in these measures. Subjects will take the SwallowStrong® device home with them and will complete 20 repetitions of the exercise (10 repetitions at the front sensor; 10 repetitions at the back sensor), three times per day on three days per week for twelve weeks. It will take approximately 10 minutes to complete 20 repetitions of the exercise resulting in about 30 minutes total for each home exercise session. During week one of the regimen, the target value of each repetition will be 60% of the 1RM. For the remaining eleven weeks of the program, the target value will be increased to 80% of the 1RM. These values of 60% and 80% were chosen based on previous work that employed progressive resistance training for the limbs and lingual musculature with healthy elders and patients post-stroke. At weeks three, five, seven, nine, and eleven, the baseline will be re-measured by phone and the 80% target value re-calculated. In addition, check-in phone calls also will be scheduled the other weeks of the study period.

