## **Statistical Analyses**

Prior to data analyses, the data collected under this study will be combined with data from its VA counterpart (IRB #2014-0939). Statistical analyses will be performed using this combined data set.

**Aim 1:** A repeated measures analysis model will be used to model changes in tongue strength in treatment and control groups, adjusted for age, gender, and baseline tongue strength. Each subject will have three observations: change between baseline and 8 weeks, baseline and 12

weeks, and 8 weeks and 12 weeks. This model will allow for comparison of differences between a) treatment durations (dose response) and b) between control and treatment groups.

**Aim 2:** Changes in oral intake and swallowing quality of life between baseline and 8 weeks, baseline and 12 weeks, and 8 weeks and 12 weeks will be modelled in a repeated measures analysis on treatment, adjusting for age, gender, and baseline outcome.

**Aim 3:** Change in number of new pneumonia diagnoses and number of hospital readmissions over a 1 year period, pre and post-study, will be modelled in linear regression models on treatment, adjusting for age, gender, and pre-study outcome.

All analyses will be performed on a randomized, or intention to treat basis, regardless of the actual treatment received. Study dropout by the subject will result in inclusion of incomplete data for that patient.

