#### Sample size calculation:

Due to funding restrictions, we propose a sample size for this pilot study of 15 subjects per group. We plan to enroll 40 subjects to account for dropout of patients who do not meet the radiographic criteria for dysphagia on their initial videofluoroscopic swallowing examination.

Previous data have been collected on the proposed treatment and measurement device through our Swallow STRONG clinic (N=40). These data have shown changes in maximum isometric lingual pressures at the front and back sensors of the MOST® device over 8 weeks of DF I-PRO therapy. The

mean difference in pressure between baseline and 8 weeks was 103 hectopascals (hPa) (SD=100 hPa) at the front sensor, and the mean difference in pressure at the back sensor was 90 hectopascals (SD=94 hPa). If we assume an SD=100 hPa for treatment and control groups, with a sample size of 15 per group, the power to detect a difference, based on a 2-sample t-test, is shown in Table 2. For the treatment group we can expect an improvement of 100 hPa on average. For a control group with no strength training, we might expect an improvement of 20 hPa. This would give us approximately 56% power to detect a difference, which is adequate for a pilot study. All analyses will be conducted in SAS (SAS Institute, Cary NC).

Table 2: Power to detect a difference between treatment/control groups, SD = 100, alpha=0.05	
Difference between case/control mean change	Power
100 hPa	75%
80 hPa	56%
60 hPa	35%
40 hPa	18%

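### The 8- versus 12-week comparison contrasts visits, not randomised durations, and Aim 1 names no control-adjusted contrast for it

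*Combined protocol and SAP*

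**What the plan says.** **Design.** The Intervention section has patients "randomly assigned into one of two groups: 1) a control group that will be receiving compensatory treatments only or 2) 12-week DF I-PRO therapy" with compensatory treatment added. The Group 2 description prescribes exercise "three times per day on three days per week for twelve weeks". No one is assigned to stop at 8 weeks. After the 8-week examination, patients in either arm whose dysphagia has resolved leave the study, and the rest go on: "If a patient in either group remains dysphagic at the 8-week visit, s/he will continue participation" to the 12-week assessment.

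**Hypotheses (Specific Aims).** Hypotheses 1a and 2a name the control group. Hypothesis 1b does not: it predicts, for treated subjects, "improvements in swallow physiology and bolus flow measures at the 12 week duration compared to 8 weeks". Hypothesis 2b does not either: "Twelve weeks of DF I-PRO therapy will result in greater improvements" than the 8-week duration.

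**Analysis (Statistical Analyses).** The Aim 1 model covers both groups and takes three change scores per subject (baseline to 8, baseline to 12, and 8 to 12 weeks). The plan then says: "This model will allow for comparison of differences between a) treatment durations (dose response"), with control versus treatment as item b). No treatment-by-interval term or contrast is named. For Aim 2 the same three changes are regressed on treatment in a repeated measures analysis.

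**Expected recovery.** Entry is allowed up to 6 months after stroke. The sample size section expects a control group without strength training to gain 20 hPa.

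**The concern.** A dose-response claim about duration needs patients who received different durations and are otherwise comparable. Here the two durations are two visits of one arm, so weeks of therapy and weeks since stroke increase together. If item a) is estimated in treated subjects, as Hypothesis 1b is worded, any improvement that would have occurred anyway between weeks 8 and 12 is counted as the effect of longer therapy. If it is instead estimated as an interval effect pooled over both arms, it is not a treatment-duration effect, because controls receive no strengthening.

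Dose response is part of the study's stated goal, and the background calls knowledge of the ideal duration critical. It motivates a longer programme by the fact that patients were still improving when an 8-week programme ended. That observation has the same ambiguity. Hypotheses 1b and 2b could be declared supported when only time has passed.

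**Working it through.** **1. The plan's own figure.** Table 2 ("Power to detect a difference between treatment/control groups, SD = 100, alpha=0.05") reproduces. For a two-sided two-sample t-test with 15 per group, the noncentrality is d / (100 × √(2/15)) = d / 36.5 on 28 df. For d = 100, 80, 60 and 40 hPa, power is 75.3%, 56.2%, 35.5% and 18.5%, against the stated 75%, 56%, 35% and 18%. The table covers treatment versus control only. No power is given for 8 versus 12 weeks.

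**2. What each contrast estimates.** The three change scores carry two independent pieces of information: (baseline to 12) minus (baseline to 8) is the 8-to-12-week change. In subjects seen at both visits, let R be recovery in weeks 8–12, T the effect of therapy given in those weeks, and C any continuing effect of the first 8 weeks.

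- Treated-arm change: R + T + C.
- Control-arm change: R.
- Between-arm difference: T + C, provided R is the same in both arms.
- Twelve weeks versus stopping at 8: (R + T + C) minus the change after stopping. The last term is never observed.

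The treated-arm estimate is therefore biased by the whole of R, whatever the SD. The between-arm difference removes R but compares continued therapy with no strengthening, not 12 weeks with 8.

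**3. Size for a treated-arm test of tongue pressure.** Inputs:

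- n: "we propose a sample size for this pilot study of 15 subjects per group". I use 10 to 15, the lower figure being an assumed allowance for exits at week 8.
- R: the plan gives 20 hPa for controls. No interval is attached to it, but the adjoining text concerns 8-week changes. At a constant rate, 20 × 4/8 = 10 hPa in four weeks. This is an assumption, with range 5–20.
- SD of the four-week change: not given. The plan's SD is 100 hPa, taken from the 8-week change. I use 100 and 50.
- T + C = 0.

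For a one-sample t-test, two-sided 5%, the noncentrality is R / (SD/√n) on n − 1 df. For R = 10 and n = 15 it is 10/25.8 = 0.39 at SD 100 and 10/12.9 = 0.77 at SD 50. Rejection rates, nominal 5%:

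| R (hPa) | SD 100, n = 10 | SD 100, n = 15 | SD 50, n = 10 | SD 50, n = 15 |
|---|---|---|---|---|
| 5 | 5.2% | 5.4% | 5.9% | 6.5% |
| 10 | 5.9% | 6.5% | 8.8% | 11.2% |
| 20 | 8.8% | 11.2% | 20.5% | 30.3% |

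At R = 10, rejections that favour longer therapy (nominal 2.5%) are 4.7–5.5% at SD 100 and 8.2–10.8% at SD 50.

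**4. The between-arm contrast.** With equal R in both arms the bias is zero and the error rate 5%; simulation with 15 per arm agrees (4.9–5.1%). Its standard error is √2 = 1.41 times larger: 36.5 against 25.8 hPa at SD 100 with n = 15. Power for a true extra 40 hPa (illustrative, the smallest difference in Table 2) with 15 per arm is 56% at SD 50 and 18.5% at SD 100.

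**5. Who contributes.** Week-12 values exist only for subjects still dysphagic at week 8. Treatment is meant to change that status, so those who remain may differ between arms and R need not be equal in them.

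**The case against.** The strongest reply is that the control needed is already there. Still-dysphagic controls are followed to week 12 and sit in the Aim 1 model, and no treated-arm-only test is written down. This stands in part. A reader might infer that recovery is bound to be reported as benefit. The documents support only that it can be, because the contrast is left unspecified rather than specified wrongly.

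A reader might also treat Aim 2 as having the same fault. Its changes, including 8 to 12 weeks, are modelled on treatment, which comes close to the contrast wanted. What remains is that Hypothesis 2b claims 12 weeks beats 8, and no analysis of this design can show that.

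A third inference would be that 12 weeks will be carried into the larger trial on this evidence. The plan says only that the results will inform its sample size.

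Finally, the numerical effect is small at the one SD the plan gives: 5.9–6.5% against 5% when R is 10 hPa. That is correct, and the larger rates need a smaller SD or faster recovery. But a modest rejection rate reflects a noisy test; it does not make the estimate unbiased.

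**Conclusion.** The point holds as a matter of specification and wording. The design has no 8-week duration to compare with 12, yet the plan presents a comparison of visits as dose response. For Aim 1, with no treatment-by-interval contrast named, recovery can pass for benefit of longer therapy. For Aims 1 and 2 alike, superiority of 12 weeks over stopping at 8 is not identifiable.

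The bias in a treated-arm estimate equals the recovery in weeks 8 to 12, about 10 hPa if the plan's 20 hPa accrues evenly over 8 weeks. The rejection rates rest on that assumption and on assumed four-week SDs, and they apply to tongue pressure only. The documents give no comparable figures for oral intake or quality of life.

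This should be fixed, but it does not threaten the trial's main result: the treatment-versus-control comparison at 8 weeks, on which the power table rests, is unaffected.

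**What to change.** 1. For Hypotheses 1b and 2b, pre-specify the between-group difference in the 8-to-12-week change (the treatment-by-interval contrast), using the controls already measured, and label it exploratory.
2. Replace the dose-response and 12-versus-8-week wording in the aims, hypotheses and analysis section with *change during continued treatment versus control*. Make no claim that 12 weeks is superior to stopping at 8.
3. State three limits with the result. It covers only subjects still dysphagic at week 8. That selection happens after randomisation and may differ between arms, so the contrast is not protected by randomisation. It includes carry-over from the first 8 weeks. Report the number leaving at week 8 in each arm.

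The cost is wording and one contrast in a model already planned, with no new arm, visits or data. The downside is an interval about 1.4 times as wide as the treated-arm one and a weaker claim. A randomised comparison of durations would be out of scale for this pilot: 80% power for 40 hPa needs n = 2 × (1.96 + 0.84)² × (SD/40)², or 25 per arm at SD 50 and 99 per arm at SD 100.

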## **Background and Significance**

**Prevalence:** Every 40 seconds, on average, someone in the United States experiences a stroke.

Due to the advancing age of the US population, by 2030, an estimated four million additional people will have had a stroke, a 21.9% increase in prevalence from 2013. Dysphagia is estimated in up to 76% of acute stroke patients and is known to increase the risk for critical post-stroke health sequelae, including pneumonia, malnutrition, dehydration, and mortality.

**Complications:** Developing pneumonia post-stroke results in a significantly increased relative risk (2.99) of death within 30 days of hospital discharge. Those patients who experience aspiration are *seven* times more likely to develop pneumonia than those who do not aspirate. Relatedly, patients with dysphagia following stroke experience significant decreases in quality of life, increased eating dependency, diminished rehabilitation potential, and longer hospital stays.

**Swallowing physiology:** Videofluoroscopic findings in patients post-stroke include poor tongue control, increased bolus transit times, reduced laryngeal closure duration, decreased and/or incomplete laryngeal elevation, and higher (worse) penetration-aspiration scale scores compared to controls. Sensory deficits also are common following stroke leading to silent aspiration. Oral sensory deficits also may occur making it difficult for a patient safely to control the bolus or to initiate a swallow.

**Tongue strength:** Swallowing consists of a series of pressure changes that begin at the lips and the muscular tongue is a major propulsive force during the swallow. Pressures produced when the tongue contacts the palate play a critical role moving the bolus through the oropharynx and into the esophagus. Patients with dysphagia post-stroke have lower average maximal isometric tongue pressures than those without dysphagia. Tongue pressure production has been found to be closely related to post-stroke dysphagia.

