*Saliva Analyses:* Each measure of viscoelasticity and lubrication properties will be recorded three times per sample. Apparent viscosity will be determined using a TA Discovery, HR-2 rheometer (TA Instruments, New Castle, DE, USA) equipped with a Peltier plate temperature control unit (233212.902). All measurements will be carried out with a flat plate geometry with a diameter of 20 mm and an operating gap of 200 µm. Each sample will first be allowed to equilibrate for 30 seconds at 37°C on the rheometer stage. Viscosity will then be measured at 37°C at shear rates ranging from 0.1 to 100 1/s. In [name] laboratory, samples will be frozen until all have been collected. Then, an enzyme-linked immunosorbent assay (ELISA) will be completed in order to quantify levels of the protein Substance P within the samples.

**Hospital Readmissions and Pneumonia Diagnoses:** The number of pneumonia diagnoses and overall hospital readmissions will be compared for the same period of time prior to enrollment and following completion of the study (up to 9 months) for each subject. Discharge reports will be used to tally the number of readmissions and clinic notes will be reviewed to determine number of pneumonia diagnoses (community, hospital-acquired, and aspiration pneumonia) for each subject.

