### **Study Timeline**

We estimate achieving our target enrollment in 9 months and completion of the project within the specified 12-month period as outlined below in Table 1. Patients will be referred from the UWHC Neurology Department where approximately 500 ischemic stroke patients are seen yearly. This large volume of patients ensures that 40 subjects will be easily accessible for recruitment into the proposed study.

Tasks	1/1/2015-12/31/2015			
	Q1	Q2	Q3	Q4
Database build & training of study staff	→			
Subject enrollment	→	→	→	
Study close out, data analysis				→

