protocols will be recorded only by this code number. The link connecting the subject and code number will be password-protected stored separately in electronic format on the password-protected hospital network and only the PI ([name]) will have access. Only the approved project research staff ([name], [name]) will have access to the coded study data. All information about the subject will be treated confidentially and will not be revealed unless required by law. All HIPAA regulations pertaining to protection of participants and eliminating identification will be followed. Data will be de-identified at the close of the study. Any breach of confidentiality will immediately be reported to the IRB. Individual medical records will be accessed twice during the one year duration of this study: once by [name] initially to confirm the subjects' eligibility for the study and then again at the end of the study (one year point) to determine number of pneumonia diagnoses and hospital readmissions for the same number of months pre- and post-enrollment. Results of study-related procedures performed solely for research purposes (not standard of care) will not be placed in the subjects' medical record.

*Videofluoroscopic Swallowing Assessment:* Subjects are at risk for aspirating during the VFS assessment. If aspiration occurs during the VFS assessment, the particular bolus condition will be terminated once the cause of the aspiration is determined. Following completion of the study protocol, compensatory approaches to treatment (e.g., postures, diet modification) may be attempted in order to determine which strategies are most effective in reducing or eliminating the occurrence of airway penetration and/or aspiration, thereby ensuring safety with swallowing for patients in both treatment groups.

Subjects will be exposed to radiation exposure equivalent to one to two years of background radiation (less than 2.5 minutes) during the videofluoroscopic swallowing study. The risks of that amount are considered to be very small, and there is no indication of harmful effects to an individual. Subjects will not be included if they are pregnant. Radiation exposure during the VFS assessment will be limited as much as possible through attention to time restraints and adherence to ASHA's Guidelines for Speech-Language Pathologists Performing Videofluoroscopic Studies. Protective apparel with lead-shielding (lead apron, thyroid shield) will be worn at all times.

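### Aim 3 labels its event-count change as one-year, but nobody can be followed for a year after completion and the linear model ignores time observed

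*Combined protocol and SAP*

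**What the plan says.** The combined protocol and SAP describes the Aim 3 counting window in three ways.

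- **Statistical Analyses, Aim 3.** The outcome is "Change in number of new pneumonia diagnoses and number of hospital readmissions over a 1 year period, pre and post-study", and it "will be modelled in linear regression models on treatment, adjusting for age, gender, and pre-study outcome". There is no offset, rate or months-observed term.
- **Data Reduction and Analysis (and, in substance, Outcomes).** Events are "compared for the same period of time prior to enrollment and following completion of the study (up to 9 months) for each subject". The window is specific to the subject, starts after completion and is capped.
- **Data Safety and Monitoring, Confidentiality.** Records are opened at screening and "then again at the end of the study (one year point) to determine number of pneumonia diagnoses and hospital readmissions", here "for the same number of months pre- and post-enrollment". This can be read as starting the later window at enrollment rather than at completion.

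The calendar is in Study Timeline: "We estimate achieving our target enrollment in 9 months and completion of the project within the specified 12-month period". Table 1 runs from 1 January to 31 December 2015, with enrollment in the first three quarters. Under Intervention, subjects still dysphagic at 8 weeks continue to week 12, and those whose dysphagia has resolved leave at 8 weeks.

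The plan gives no baseline event rate, no power for Aim 3, and no rule for a subject who dies or whose records stop.

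**The concern.** A difference in event counts has meaning only together with the time over which events were counted. Here that time appears to vary widely between subjects, because enrollment is spread over nine months and the records are read on one date. The model treats a count from a few days and a count from nine months as the same kind of observation. The pre-study count used as covariate covers an equally variable window.

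The Project Summary and Specific Aims say the pilot's results will be used to size a larger trial. A coefficient described as a one-year change, but estimated over much shorter mixed windows, would mislead that calculation.

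Death or loss of records also shortens the window without adjustment. Background and Significance notes that pneumonia after stroke carries a "significantly increased relative risk (2.99) of death within 30 days of hospital discharge", so the question is not idle in this population.

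**Working it through.** **1. The plan's own power figure.** Table 2 concerns tongue pressure only. A two-sided two-sample t-test with 15 per group, SD 100 hPa and difference 80 hPa gives 56.2%, against the stated 56%. The other rows reproduce too (75.3%, 35.5%, 18.5%). None of this bears on Aim 3, so every event rate below is an assumption.

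**2. Time available on the stated calendar** (records read 31 December 2015; months = days / 30.4375).

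| Enrolled | Clock starts | Days to 31 Dec | Months |
|---|---|---|---|
| 1 Jan | 12-week visit, 26 Mar | 280 | 9.2 (capped at 9) |
| 30 Sep | 12-week visit, 23 Dec | 8 | 0.26 |
| 1 Jan | 8-week exit, 26 Feb | 308 | 10.1 (capped at 9) |
| 30 Sep | 8-week exit, 25 Nov | 36 | 1.2 |
| 1 Jan | enrollment | 364 | 12.0 |
| 30 Sep | enrollment | 92 | 3.0 |

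No row gives a year after completion. The longest window that every subject could complete is about 8 days after a 12-week visit, or 3 months from enrollment.

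**3. Average window.** Assume uniform accrual over 9 months and a 12-week completion (84 / 30.4375 = 2.76 months). The mean is 12 - 4.5 - 2.76 = 4.74 months, with SD about 2.6. The share with under 3 months is (9 - 6.24) / 9 = 31%, where 6.24 = 12 - 2.76 - 3.

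**4. What the coefficient estimates.** Assume 1.2 control events per year and a rate ratio of 0.5. The true effect is -0.6 events per year. Over the average window the expected difference is -0.6 x 4.74 / 12 = -0.24, and simulation of the planned model gave the same value. That is about 40% of the annual effect, and the fraction is set by the accrual calendar.

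**5. Power and test size.** Simulation: 15 per arm, 6,000 runs per scenario, equal pre and post windows capped at 9 months, age and gender omitted. The planned regression is compared with a Poisson score-type test using a person-time offset, robust variance and the pre-count. The ratio 0.21 is 1 - 0.79, from the uncontrolled cohort's fall in admissions given in Background.

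| Control rate per year | Rate ratio | Overdispersion (gamma variance) | Planned | Offset test |
|---|---|---|---|---|
| 0.3 | 0.5 | 0 | 4.1% | 4.0% |
| 0.6 | 0.5 | 0 | 8.6% | 8.8% |
| 1.2 | 0.5 | 0 | 15.8% | 17.1% |
| 2.4 | 0.5 | 0 | 26.0% | 29.0% |
| 1.2 | 0.5 | 1 | 11.1% | 11.4% |
| 2.4 | 0.5 | 1 | 18.1% | 18.3% |
| 1.2 | 0.21 | 0 | 40.0% | 42.3% |
| 2.4 | 0.21 | 0 | 67.8% | 73.0% |

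The gain here is 0 to about 5 points. A separate simulation at rate ratio 0.3 gave 11-38% for the planned model and 15-44% for a rate-based permutation test, a gain of about 4 to 6 points. The planned model's type I error was 2.8% to 4.8%.

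Dividing each subject's count by months and analysing it unweighted does worse than the plan: 12.9% against 15.8% at 1.2 per year, rate ratio 0.5, no overdispersion.

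**6. Exposure that could differ by arm.** Leaving at 8 weeks adds 28 days of post-completion window. If resolution differed by an assumed 20 points, the mean window would shift by 0.20 x 28 = 5.6 days, or 0.18 months, about 4% of 4.74.

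**The case against.** The best defence is that the plan does give time bases. Aim 3 names a year, and the other sections match pre and post length within each subject. If one fixed, fully observed window were adopted, the linear coefficient would be a mean difference per window and the unequal-exposure argument would fall away. The 31% under three months also depends on starting the clock at the 12-week visit: counted from enrollment, everyone has at least about three months. The calendar is itself an estimate, and this is the third aim of a pilot with no power target for it.

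All of that stands, and it rules out several stronger readings that a reader might infer.

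- **That the analysis has no time base.** It has three that conflict.
- **That the comparison is biased or the test invalid.** Randomisation balances enrollment date in expectation, and the simulated size stays below 5%. The 8-week exits are an exception in principle, but a small one.
- **That unequal follow-up costs substantial power.** The documents give no event rate, and the loss is small over the rates tried, partly because the pre-count over the same window carries window length. Power is low chiefly because events are few: about 3 to 21 in total at rate ratio 0.5.
- **That early death will make an arm look better.** It could, but subjects need physician approval of medical stability, no death rate is given for them, and the size is unknown.

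The defence does not rescue the stated year, which the calendar rules out. Nor does matching within subject make windows equal between subjects, which is the comparison the model makes.

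**Conclusion.** The point holds as one of estimand and interpretation. Followed as written, Aim 3 produces a coefficient described as a one-year change that is really a count difference over windows from about 0.3 to 9 months after completion (mean about 4.7), or 3 to 12 months from enrollment. It cannot be read per year or carried into planning the larger trial.

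The ranges rest on the Study Timeline dates and the single record read; the mean also assumes uniform accrual and 12-week completion. The 40% illustration and the power comparison (a gain of 0 to about 5-6 points) rest on assumed event rates. The change should be made, but nothing here shows that the between-group test is invalid.

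**What to change.** - Reconcile Outcomes, Data Reduction and Analysis, Confidentiality, and Statistical Analyses to one attainable window with a stated start and maximum length, and remove the one-year label.
- Replace the linear models with a Poisson-type rate model with log months observed as offset, adjusted for age, gender and the pre-study rate or count. Use overdispersion-robust variance, or a p-value from re-randomisation under the allocation scheme actually used.
- Do not use unweighted per-subject rates as the outcome.
- End each subject's observation at death, last record or the end of the window, with last record defined in advance. Report person-time, events and deaths by group.

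The cost is SAP wording, a short program and dates from records already being reviewed; no new visits or subjects are needed. The result becomes a rate ratio, and its interval will be wide.
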